2 STUDY OVERVIEW AND OBJECTIVE

2.1 Study Overview

This is a single-arm, open label, phase I/II study of CT-011 in combination with lenalidomide in adult (age 18 years and older) patients with relapsed MM. A 4-cohort, dose-escalation, phase I portion will

be completed with the primary endpoint to determine safety and tolerability, seeking maximally tolerated doses (MTDs) of each agent in combination in a standard 3+3 design over 4 dose levels of 1.5, 3, 3, and 6 mg/kg of CT-011 given intravenously every 4 weeks (every 28 days), and lenalidomide given at 15, 15, 25, and 25 mg orally daily on days 1-21 of a 28-day cycle. A minimum of 12 and a maximum of 30 patients will be recruited for the phase I portion of the study. Upon identification of the MTD for the dose level combination of CT-011 and lenalidomide, the phase II portion of the study will commence accruing an additional 23 patients to assess the primary endpoint of overall response rate after 4 cycles by the IMWG criteria. Secondary endpoints include assessment of overall response rate after 8 and 12 cycles of therapy, progression-free survival, pharmacokinetic and pharmacodynamics data, immunomonitoring of lymphocyte subsets, including T and NK cell subsets, and *ex vivo* immune functional assays. For both phases, Dexamethasone 40 mg orally weekly may be added if only stable disease after 3 cycles. Dexamethasone can be reduced to 20 mg based on tolerability or if patient is 70 years or older.

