Previous studies of lenalidomide alone in a similarly defined relapsed/refractory MM patient population has shown an overall response rate of 25%, which also included the addition of dexamethasone after 2 cycles to non-responding stable disease patients. We will consider this regimen promising if the true overall response rate is 50% or greater when lenalidomide is combined upfront with CT-011. Therefore, we will test the null hypothesis that the true overall response rate (ORR) is at most 25% (reflecting a combination regimen ORR that would not be of interest) versus our alternative hypothesis that the true ORR in patients treated with this combination regimen is at least 50%.

Decision Rule: The largest response rate where this treatment regimen would be considered ineffective in this population is 25%, and the smallest response rate that would warrant subsequent studies with this proposed regimen in this patient population is 50%. The following Three-Outcome phase II study design is a modification of the standard one-stage phase II design and uses a maximum of 29 evaluable patients to test the null hypothesis that the true response rate is at most 25%. Since we will include the 6 patients treated at the MTD from the phase I portion of the trial, this will require accruing an additional 23 evaluable patients for this phase of the study. Based on this study design, there are three possible outcomes:

- **Not promising**: This regimen will be classified as not promising with respect to the response rate in this patient population if at most 9 patients have any response after 4 cycles of therapy out of the total 29 evaluable patients.
- **Promising**: This regimen will be classified as promising with respect to increasing the response rate in this patient population if at least 12 patients have an observed response to treatment after 4 cycles of therapy out of the total 29 evaluable patients. Subsequent larger confirmatory studies may be warranted.

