- **Inconclusive**: The results of this study will be classified as inconclusive with respect to this regimen demonstrating an improved response rate if only 10 or 11 of the 29 total evaluable patients have a response after 4 cycles of therapy. In this case, other factors such as progression-free survival, toxicity, and correlative outcomes will be used in addition to the response data to make the final determination as to whether or not this treatment is considered promising and worthy of further study in this patient population.

In this type of three-outcome phase II design with an uncertainty region, the associated errors are not the same as in the standard phase II study designs. In this study, the type I and type II error rates are constrained at 4% and 3%, respectively; The other parameters included in this type of design are eta (the probability of determining that a regimen is not worth pursuing further when it truly is not effective) and pi (the probability of determining that a regimen is promising when it truly is). Under this design, eta=0.83 and pi=0.87.

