The proportion of responses (partial and complete) will be calculated out of all eligible patients who receive any treatment in that disease group who are included in the phase II assessment. Assuming the number of responses is binomially distributed, 95% binomial confidence intervals will also be calculated for the estimate of the proportion of responses. All adverse events will be summarized by the NCI CTCAE v. 4 criteria, and tabulated across all patients who received any treatment with a focus on severe (grade 3+) adverse events and toxicities (i.e. those deemed at least possibly related to study treatment). In addition, we will summarize the proportion of patients who received dexamethasone after being stable disease but without response after 2 cycles of therapy. We will descriptively summarize how many of these patients were converted to response after the addition of dexamethasone. Since the addition of dexamethasone is part of the overall treatment regimen that is dependent on treatment outcome at a certain time point, we will not make other adjustments to the study design to evaluate these patients separately outside of this descriptive summarization of whether or not they received the dexamethasone. We will evaluate other clinical outcomes such as progression-free survival and overall survival using the methods of Kaplan-Meier, although these analyses will be exploratory and primarily to help describe the cohort itself.

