6.3 Clinical outcome definitions

Time to progression: TTP will be defined as the time from start of treatment until the date he or she has progression or dies. Any subject who has received study treatment but has neither progressed nor died will be censored on the date of his or her last tumor assessment. A subject who has not received study treatment and who has neither progressed nor died will be censored on the day he or she was enrolled.

Progression Free Survival: PFS will be defined as the time from study entry until disease progression or death at trial closure for the per protocol population. Patients who withdraw from the trial prior to disease progression and who are either lost to follow-up, die or who begin alternative treatments prior to progression, will have their data censored as of the date considered to be lost to follow-up, date of death, or the first day of alternative therapy.

Time to Response: A subject's time to response is defined as the time from first dose of study therapy until measurement criteria are first met for [VG]PR or CR or SD (whichever status is recorded first). Time to response is computed only for subjects whose best response is [VG]PR or CR.

Duration of Overall Response: The duration of overall response will be computed for subjects whose best response is either [VG]PR or CR or SD. It will be measured from the time measurement criteria are first met for complete response or partial response (whichever status is recorded first) until the first date of progressive disease or death. Subjects who neither progress nor die will be censored on the date of their last tumor assessment.

Overall Survival: A subject's survival time will be defined as the time from start of treatment to the date of his or her death. If the subject has not died, survival will be censored on last date the subject was known to be alive.

Response Rate: The tumor response rate will be defined as the total number of subjects whose best response is PR or VGPR or CR or SD, divided by the number of per protocol patients.

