7.0 REGISTRATION PROCEDURES

7.1 Registration Guidelines

Eligible patients will be entered on study centrally at The Ohio State University. OSU patients will be registered by the OSU Clinical Research Coordinator/Specialist. Subsite patients will be registered by the OSU Subsite Coordinator.

Following registration, patients should begin protocol treatment within 72 hours. Issues that would cause treatment delays should be discussed with the Principal Investigator. If a patient does not receive protocol therapy following registration, the patient's registration may be canceled, pending approval by the Principal Investigator who will determine whether the patient will be replaced. Patients that do not receive any protocol therapy will not be evaluable for toxicity or response.

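### Section 6.3 defines Response Rate so that stable disease counts as response, over an undefined per-protocol set, in contradiction to 6.1.2 and Appendix B

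*Combined protocol and SAP*

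**What the plan says.** Section 6.3 (Clinical outcome definitions) has one entry for response rate. It counts "subjects whose best response is PR or VGPR or CR or SD, divided by the number of per protocol patients". The term per protocol is used as an analysis set in one other place, the PFS definition in the same section, and no section says who belongs to it.

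Section 6.1.2 (Phase II portion) describes the primary analysis differently: "The proportion of responses (partial and complete) will be calculated out of all eligible patients who receive any treatment". The same paragraph refers to patients given dexamethasone "after being stable disease but without response", and plans to describe "how many of these patients were converted to response after the addition of dexamethasone". The decision rule calls the regimen promising "if at least 12 patients have an observed response to treatment after 4 cycles of therapy out of the total 29 evaluable patients", inconclusive "if only 10 or 11 of the 29 total evaluable patients have a response after 4 cycles of therapy", and not promising at 9 or fewer. The only statement on evaluability is in 7.1: "Patients that do not receive any protocol therapy will not be evaluable for toxicity or response".

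Three other places separate SD from response. The synopsis (Study Design) and 4.3 both equate having responded with complete or partial response and list stable disease as a separate alternative. Appendix B defines SD as failing the criteria for CR, VGPR, PR and progression, and its note e advises against SD as an indicator of response.

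Two neighbouring definitions in 6.3 also include SD. Time to Response may stop when SD is first recorded, yet it is computed only for patients whose best response is [VG]PR or CR. Duration of Overall Response is computed for patients whose best response is SD as well, yet its clock starts at complete or partial response.

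**The concern.** The statistical section holds two incompatible definitions of the phase II efficacy measure. They differ in three ways:

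- **Numerator:** PR or better in 6.1.2; SD or better in 6.3.
- **Denominator:** eligible treated patients in 6.1.2; an undefined per-protocol set in 6.3.
- **Timing:** response after 4 cycles in 6.1.2; best response in 6.3.

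A rate reported under 6.3 would be a disease-control rate under the name of response. It could not be set against the 25% null rate. The single-agent lenalidomide figures in 1.3.1 are 25% (complete, partial or minor response) and 26% (complete and partial), and neither includes SD.

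The two lesser definitions do not work on their own terms. A patient who passes through SD before PR gets a time to response that ends before any response. A patient whose best response is SD has no start date for duration of response.

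**Working it through.** **1. Reproduce the plan's design figures.** Inputs from 6.1.2: n = 29, null rate 0.25, alternative 0.50, not promising at 9 or fewer, promising at 12 or more. With X the number of responders, exact binomial:

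| Quantity | Formula | Result | Stated in 6.1.2 |
|---|---|---|---|
| Type I | P(X ≥ 12; 29, 0.25) | 0.0390 | 4% |
| Type II | P(X ≤ 9; 29, 0.50) | 0.0307 | 3% |
| eta | P(X ≤ 9; 29, 0.25) | 0.8337 | 0.83 |
| pi | P(X ≥ 12; 29, 0.50) | 0.8675 | 0.87 |

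All four agree with the stated values after rounding. The rule is therefore calibrated to response rates of 25% and 50%, with response meaning PR or better as 6.1.2 says.

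**2. Set the definitions side by side.**

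| Place | Is SD a response? | Denominator |
|---|---|---|
| 6.3 Response Rate | Yes | Per-protocol patients (undefined) |
| 6.1.2 analysis paragraph | No | Eligible patients who received any treatment |
| 6.1.2 decision rule | Not stated separately | 29 evaluable patients |
| Synopsis and 4.3 | No | Not applicable |
| Appendix B, SD row and note e | No | Not applicable |

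Section 6.3 stands alone on the numerator.

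**3. Effect on a reported rate (illustrative counts).** Take 7 patients with PR or better and 5 with SD. The 6.1.2 numerator gives 7/29 = 24.1%. The 6.3 numerator over the same 29 patients gives (7 + 5)/29 = 41.4%. Here 29 is borrowed from 6.1.2 to isolate the numerator; the true 6.3 denominator cannot be calculated because its set is undefined.

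**4. What would follow if the 6.3 numerator entered the decision rule.** This is hypothetical, because 6.1.2 does not use that numerator. With a true PR-or-better rate of 0.25 and an SD share s, the chance of a promising result is P(X ≥ 12; 29, 0.25 + s). The documents give no SD share, so s is assumed:

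| s | 0 | 5% | 10% | 15% | 20% | 30% |
|---|---|---|---|---|---|---|
| P(promising) | 0.039 | 0.13 | 0.30 | 0.51 | 0.72 | 0.95 |

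**5. Effect of keeping unassessed treated patients in the denominator.** Keep the 9 and 12 cut-offs and count unassessed patients as non-responders. If 1 or 2 of the 29 are unassessed (assumed), X is binomial on 28 or 27:

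| Assessed | Type I | Type II | pi |
|---|---|---|---|
| 29 | 0.039 | 0.031 | 0.868 |
| 28 | 0.029 | 0.044 | 0.828 |
| 27 | 0.022 | 0.061 | 0.779 |

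**The case against.** The strongest reply is that 6.3 governs very little. Section 6.1.2 gives the primary rule its own numerator and time point, so a careful analyst would apply it correctly. Section 2.1 says "Secondary endpoints include assessment of overall response rate after 8 and 12 cycles of therapy", and the sentence before it ties overall response rate to the IMWG criteria. Section 2.3 and the synopsis do the same for the assessments at 8 and 12 months. The comparison of marker changes by response, and the count of patients converted after dexamethasone, both sit in 6.1.2 and naturally take its meaning. The PD-L1 correlation in 8.4 is the one analysis that names response rate without a numerator of its own, and it is conditional on sample size. Time to Response and Duration of Overall Response are not listed endpoints.

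All of this stands, and it limits the reach of the point. A reader might infer that the trial's type I error is inflated to 0.30 or more. The documents do not support that: the figures in step 4 require an analyst to override 6.1.2. Nor do they support the view that every later response analysis falls under 6.3.

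A reader might also infer that 6.1.2 contradicts itself on the denominator. It uses two labels, but 7.1 excludes only untreated patients from evaluability, so the 29 evaluable patients and the eligible treated patients can be the same people. One sentence would settle it.

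The reply does not remove the contradiction. Section 6.3 is the section that sets out to define the clinical outcomes, and nothing there marks its response rate as a separate disease-control measure.

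**Conclusion.** The 6.3 definition is wrong as written and should be corrected, along with Time to Response and Duration of Overall Response. The contradiction rests on the text alone and needs no assumption.

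Its practical size is moderate. The decision rule of 9 and 12 out of 29 keeps its stated properties. The harm is a mislabelled rate, not comparable with the 25% benchmark, and two incompatible definitions of the primary efficacy measure in one statistical section. The larger probabilities in step 4 depend both on misuse of the rule and on assumed SD shares. This is a should-fix point, not one that invalidates the primary analysis.

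**What to change.** In 6.3:

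- Delete SD from Response Rate, Time to Response and Duration of Overall Response.
- Define response as sCR, CR, VGPR or PR by the IMWG criteria in Appendix B.
- Replace the per-protocol denominator of Response Rate with the 6.1.2 set: all eligible patients who received any study treatment.
- If SD or better is of interest, report it separately as disease control.

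In 6.1.2:

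- State that evaluable means that same treated set, so that treated patients without a response assessment stay in the denominator as non-responders.
- State how a confirmed response reached before the end of cycle 4 counts towards response after 4 cycles. The synopsis, 4.1 and 4.3 allow earlier assessment. Without a rule, a patient with a confirmed early PR who stops before cycle 4 could become a non-responder by default.

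The cut-offs stay as they are, and no patients or procedures are added. The reported rate will be lower than under the 6.3 text. If 1 or 2 of 29 treated patients are unassessed (assumed), pi falls from 0.868 to 0.828 or 0.779. The denominator already written in 6.1.2 implies that loss, so the correction makes it visible rather than creating it.

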6.4 Prior and concomitant treatment

The type (brand name and active ingredient) and duration of administration of all medications taken at the time of the inclusion or during the study will be recorded on the Case Report Form (CRF). Dosage, route of administration, and indication will also be specified.

6.5 Prohibited treatments

The use of concomitant chemotherapy, biological therapy (including cytokines, however erythropoietin is allowed), and steroid therapy (inhaled, oral or topical steroids for treating mild to moderate asthma, allergies or ocular inflammations, typically at ≤ 500 ug/day of fluticasone or equivalent are allowed), is prohibited as long as the patient is on the study and must have been stopped at least 4 weeks prior to first dose administration. Concomitant radiotherapy during treatment for palliation of pain may be permissible with prior approval of study PI. Radiotherapy should be directed to a localized area (involved field radiotherapy) and cannot exceed 25Gy. Radiotherapy to more than one localized area at a time is not allowed. Participation in any clinical study involving any medications or treatments, whether approved or investigational, is prohibited.

7.0 REGISTRATION PROCEDURES

7.1 Registration Guidelines

Eligible patients will be entered on study centrally at The Ohio State University. OSU patients will be registered by the OSU Clinical Research Coordinator/Specialist. Subsite patients will be registered by the OSU Subsite Coordinator.

Following registration, patients should begin protocol treatment within 72 hours. Issues that would cause treatment delays should be discussed with the Principal Investigator. If a patient does not receive protocol therapy following registration, the patient's registration may be canceled, pending approval by the Principal Investigator who will determine whether the patient will be replaced. Patients that do not receive any protocol therapy will not be evaluable for toxicity or response.

7.2 Assignment of Study Numbers

Each patient enrolled in the study will be registered in the OSU database. Each patient enrolled will be assigned a sequential study identifier by the study team.

7.3 Study Records

Study data will be collected in standardized case report forms (CRF). The investigator or designate will record all patient information, including patient identification, disease stage, previous treatment, as well as information concerning drug administration, results of laboratory tests, toxicity and efficacy data.

A specific form will be used for recording and reporting serious adverse events as defined in section 10.

7.4 Selection Procedures

All eligible patients must be registered. This must be done before the start of treatment. On receipt of all the necessary baseline information, a clinical research coordinator will assess whether the patient is eligible or not.

7.5 Subsite Patient Registration

Subsite patients will have eligibility verified and will be centrally registered at The Ohio State University by the OSU Subsite Coordinator. Subsites should call or email the OSU Subsite Coordinator to verify enrollment availability prior to consenting patients.

Following registration, patients should begin protocol treatment within 72 hours. Issues that may cause treatment delays should be discussed with the OSU Principal Investigator and OSU Subsite Coordinator as soon as possible. The OSU Subsite Coordinator must be notified immediately if a patient does not receive protocol therapy.

Only patients deemed eligible by the subsite research team should be submitted for eligibility verification and registration by the OSU Subsite Coordinator.

To request subsite patient registration, the documents below must be completed by the subsite research team and faxed to the OSU Subsite Coordinator. The OSU secure email system may be used. Contact the OSU Subsite Coordinator for more information.

Required documents for registration (refer to Supplemental Forms Document):

- Enrollment Form
- Signed Eligibility Checklis
- Source documents verifying every inclusion & exclusion criteria
- Required screening items as listed in the Protocol Calendar. Screening tests must be within the specified window.
- Signed informed consent document (and HIPAA form, if separate)
- Documentation of consent process
- Emails and other signed and dated documents used as source documentation

The OSU Subsite Coordinator will confirm receipt of the registration documents with the subsite contact listed on the Enrollment Form (refer to Supplemental Forms Document). If confirmation is not received within 2 hours, it is strongly recommended that the subsite call the OSU Subsite Coordinator to confirm registration documents were received.

Registration requests will be processed as soon as possible and no later than 1 business day after receipt of the registration documents, pending there is no additional information needed to complete eligibility verification. Registration will occur upon OSU confirmation that the patient meets eligibility criteria.

The Subsite Coordinator will securely email the subsite contact listed on the Enrollment Form (refer to Supplemental Forms Document) with the registration confirmation and the patient's assigned study number.

8.0 Correlative studies

The focus of our correlative studies will be to study the immunogenicity of CT-011 through peripheral blood studies in the following general areas:

- To assess pharmacokinetics (PK) and pharmacodynamics of CT-011 in combination with lenalidomide.
- To assess CT-011 immunogenicity and correlative biologic studies to assess immunomonitoring of lymphocytes subsets including T and NK cells and ex-vivo assessment of immune functional activities.

8.1 PK and correlative laboratory investigations

Samples for CT-011 PK determination will be collected with cycle 1 prior to CT-011 infusion, immediately at the end of the infusion, 1 hour after end of infusion, approximately 24(C1D4), 72(C1D6), 168 (C1D10) & 336 (C1D17) hrs– and just prior to cycle 2 CT-011 administration. CT-011 blood levels will be assessed with a specific ELISA technique previously validated and derived concentrations will be used to calculate PK parameters. We will compare these results with PK data obtained in the single agent phase I study previously completed to assess for any effects of co-administration of len on CT-011 PK.

We will also assess for immunogenicity at baseline and monthly starting 1 month after dose level 3 (3 mg/kg) is started. This will be done by Medivation Inc. (see Appendix G)

We will also conduct extensive immunomonitoring of T and NK cell subsets at baseline and upon completion of each 28-d cycle of therapy. We will focus our analyses principally on the absolute and relative percentage of CD8(+) T cells and CD4(+) T cell subsets including: CD4(+)C45RO(+)CD62L(-)CCR7(-) effector/memory T cells, CD4(+)CD62L(-)CD127(+) peripheral memory T cells, and CD4(+)CD25^{bright}FOXP3(+),CD127^{low/absent} regulatory T cells. We will study Th1/Th2/Th17 polarization in T cells (by expression of CD3, CD4, CD193, CD293, CXCR3, CCR4, and CD45).

